2.8 Rationale for study design

To assess the activity of a new treatment regimen, conventional phase II designs use either a single arm design compared with historical controls or a randomized design with a control arm of standard treatment, if such a standard is identified. For patients with recurrent GBMs, there are no extant standards of care. In a paradigm such as the one being studied in the proposed trial, testing each combination against historical controls would involve three separate trials, a process that will not provide timely answers to the question at hand nor allow utilization of resources in an efficient manner. To overcome some of these hurdles and test these combinations against each other as well as historical controls, this study proposes to utilize a bayesian adaptive randomization design, which will pit the three treatment regimens against each other. This will result in progressive bias of randomization towards the best of the three regimens in a single trial. The "winner" of these three regimens will be considered the best regimen for further testing in a larger trial if it compares favorably with historical controls [25, 26, 27].

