11.2 Phase II component

This is an adaptive randomized phase II trial to compare three treatment arms: a) vorinostat + Isotretinoin, b) Temozolomide + Isotretinoin, and c) vorinostat + Isotretinoin + Temozolomide, in patients with recurrent GBM. The primary outcome is Progression Free Survival (PFS). Patients will be randomized among arms using a Bayesian adaptive algorithm. Technical details of this methodology are given in Appendix H. Patients will be randomized fairly among the three arms at the start of the trial (for the first 30 patients). Thereafter, as the trial progresses and data accrue, the randomization will become unbalanced in favor of the

treatment that, on average, has better results in terms of failure time. Therefore, each successive patient is more likely to receive the treatment with better results, on average. A minimum of 30 and a maximum of 135 patients will be accrued and there will be 6 months follow up after the last patient is accrued. Based on an anticipated accrual rate between 3 and 5 patients per month, the maximum trial accrual period will be between 45 and 27 months.

Patients enrolled in the surgical arm of the phase II component will be randomized to one of the three treatment arms after surgery is performed. In surgical patients, cycle 1 will be the first cycle of treatment after surgery. PFS in these patients will be determined from the date of randomization into the chemotherapy arms (i.e. after surgery for tumor resection), and not from the date of registration in the trial.

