The tables given below summarize operating characteristics of the design. The historical median PFS is 3 months. The tables below assume an accrual rate of either 3 or 5 patients per month. The trial will be stopped early and a treatment selected as being "better" if the probability that one treatment's median PFS is larger than the other's PFS exceeds 0.975. If the trial does not stop early and the maximum 135 patients are accrued, a treatment is selected as being "better" if the probability that one treatment's median PFS is larger than the other's PFS exceeds 0.85. A treatment arm will be dropped at any point during the trial if the probability that the treatment's median PFS is larger than 3 months is less than 0.01. The "# of patients treated" row is the average number of patients treated on a given arm under the given scenario. When the medians all equal to 3 months (scenario 1), the probability of selecting one of the three arms (i.e., a false positive result) is at most 6% for both accrual rates. The probability of selecting the best treatment (i.e., a true positive result) for scenario 4, when the medians PFS are 3, 3, and 7 months for the arms, respectively, is 99.5% for the accrual rate of 3 patients per month and 99.7% for the accrual rate of 5 patients per month.

At each evaluation when a new patient is coming in the study, the data for patients who have been followed till that time and not yet progressed are accounted in the analysis.

The trial will be conducted using a website developed in the Department of Biostatistics at MD Anderson Cancer Center. Through the web interface, the users have the ability to randomize patients, update last evaluation date and current patient status. When a patient is randomized the calculations are based on all available data entered into the website. The results of the randomization are displayed to the screen for the user to view. All data is stored in a secure SQL server database.

Run Date: Wed May-05-2010 03:46:39 PM Trial Design

Primary endpoint	Time-To-Event
Number of arms	3

2006-0709 March 4, 2011 Page 48 of 57

Minimum patient accrual	30
Maximum patient accrual	135
Number of patients to randomize fairly	30
Minimum randomization probability	0.1
Tuning parameter	1
Additional follow-up	6
Goal of study	Maximize θ

Prior Parameters

Arm Name	Description	Prior Parameters (a, b)
Arm1	V+A	(2.009, 3.027)
Arm2	T+A	(2.009, 3.027)
Arm3	V+A+T	(2.009, 3.027)

Stopping Rules

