Suspend accrual to an arm if $Pr(\theta_i > max(\theta_{j \neq i}) | Data) < P_L$ Stop the trial and select an arm as superior if $Pr(\theta_i > max(\theta_{j \neq i}) | Data) > P_U$ At the final analysis select an arm as superior if $Pr(\theta_i > max(\theta_{j \neq i}) | Data) > P_U^*$ Suspend accrual to an arm if $Pr(\theta_i > \theta_{min}) | Data) < P_L^*$

Stopping Rule Details

Arm	Group	PL	Ρυ	P∪*	θ min	Pl*
Arm1	No groups	0.01	0.975	0.85	3	0.01
Arm2	No groups	0.01	0.975	0.85	3	0.01
Arm3	No groups	0.01	0.975	0.85	3	0.01

SIMULATION PARAMETERS WITH ACCRUAL OF 3 PATIENTS/MONTH

Number of patients accrued each month	3
Number of repetitions	1000
Random number generator seed	123456789

Scenario 1						
Average	Trial Length	49.5 months				
Arm	True Median Survival	Pr(Selected)	Pr(Selected Early)	Pr(Stopped Early)	# Patients (2.5%,97.5%)	
V+A	3	0.054	0.015	0.082	43.7 (11,88)	

2006-0709 March 4, 2011 Page 49 of 57

T+A	3	0.051	0.013	0.081	43.8 (11,90)
V+A+T	3	0.061	0.015	0.083	43.8 (11,89)
	·			-	-
Scenario 2	2				
Average	Trial Length	43.3 months			
Arm	True Median Survival	Pr(Selected)	Pr(Selected Early)	Pr(Stopped Early)	# Patients (2.5%,97.5%)
V+A	3	0.002	0.002	0.566	20.8 (10, 49)
T+A	4	0.038	0.018	0.301	36.7 (10, 89)
V+A+T	5	0.54	0.261	0.026	59.4 (10, 98)
	-				
Scenario 3	3				
Average	Trial Length	37.5 months			
Arm	True Median Survival	Pr(Selected)	Pr(Selected Early)	Pr(Stopped Early)	# Patients (2.5%,97.5%)
V+A	3	0	0	0.918	143(10.28)
$T+\Delta$	5	0 019	0 015	0.510	31.9 (10, 86)
$V + \Delta + T$	7	0.758	0.015	0.020	57.6 (10, 101)
VIAII	/	0.750	0.400	0.015	57.0 (10, 101)
Scenario	1				
Scenario -	*				
Average	Trial Length	21.9 months			
Arm	True Median	Pr(Selected)	Pr(Selected Early)	Pr(Stopped Early)	# Patients (2.5%,97.5%)
1/1.0	Survivai				144(10.22)
V+A	3	0	0	0.98	14.4 (10, 32)
I+A	3	0	0	0.979	14.3 (10, 32)
V+A+I	/	0.995	0.949	0	36 (10,90)
~ •	_				
Scenario :	5				
Average	Trial Length	28.6 months			
Arm	True Median Survival	Pr(Selected)	Pr(Selected Early)	Pr(Stopped Early)	# Patients (2.5%,97.5%)
V+A	3	0	0	0.935	14.3 (10, 28)
T+A	4	0.005	0.005	0.833	20.8 (10, 56)
$V + \Delta + T$	7	0.96	0.803	0.005	475(10.97)
,					
Scenario (6				
Average	Trial Length	10.3 months			
Arm		Pr(Selected)	Pr(Selected	Pr(Stopped	# Datiente
AIIII	nue	FIL Selected)	In Selected	Tert Stopped	

2006-0709 March 4, 2011 Page 50 of 57

	Median Survival		Early)	Early)	(2.5%,97.5%)
V+A	1	0.025	0.001	0.819	10.2 (10,13)
T+A	1	0.015	0	0.802	10.3 (10,13)

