T+A	4	0.003	0.003	0.803	23.7 (10,64)
V+A+T	7	0.949	0.727	0.003	53.2 (11,98)

Scenario 6

Average Trial Length 6.28 months

Arm	True Median Survival	Pr(Selected)	Pr(Selected Early)	Pr(Stopped Early)	# Patients (2.5%,97.5%)
V+A	1	0.02	0	0.768	10.4 (10,14)
T+A	1	0.022	0	0.762	10.5 (10,14)
V+A+T	1	0.024	0	0.757	10.5 (10, 15)

(Abbreviations: PFS: Progression free survival; V, vorinostat; A, accutane (isotretinoin); T, temozolomide)

Patients' demographic information at baseline will be analyzed, with data summarized in tables listing the number of subjects per treatment group in order to assess comparability. The Student t-test or the Wilcoxon rank sum test will be used to compare continuous variables between two different patient groups. The chi-squared test or the Fisher exact test will be applied to assess the association between two categorical variables.

Time-to-event outcomes, including progression-free survival and overall survival, will be estimated using Kaplan-Meier method. The log-rank test will be performed to test the difference in time-to-event distributions between patient groups. Cox proportional hazards model will be utilized to include multiple covariates in the time-to-event analysis.

Toxicity data will be summarized by frequency tables. The association between the types and severity of toxicity and the treatment groups will be evaluated. No formal statistical testing will be performed on these summary data.

To provide formal safety monitoring in the Phase II portion of the trial, after enrollment of every 10 patients into each of the three arms, we will assess the group for toxicity. If dose limiting toxicity as defined in the phase I portion of the trial is reached =/> 1/3 of patients despite dose reduction, the arm will stop accrual. If dose reduction permits continuation of treatment in these patients, the starting dose levels for the remainder of the patients on the trial will be modified to a lower starting dose (-1) level specified in the dose modification section.

For the efficacy endpoint, intent-to-treat analysis will be applied to the randomized and eligible patients. For the toxicity endpoint, as-treated analysis

will be used to include any patient who received the treatment – regardless of the eligibility nor the duration or dose of the treatment received.

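### An arm closed for toxicity can still be selected as superior on PFS and remains a comparator that the open arms must beat

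*Combined protocol and SAP*

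**What the plan says.** The safety rule stands in Sections 9.1 and 11.2. Each arm is assessed after every 10 patients. If DLT reaches one third "of patients despite dose reduction, the arm will stop accrual". If dose reduction lets those patients continue, later patients start at a lower dose level instead. Stopping accrual is the only consequence given for the closing branch.

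The efficacy rules stand under Stopping Rules in Section 11.2. The early rule ("Stop the trial and select an arm as superior if") and the final rule ("At the final analysis select an arm as superior if") use the same quantity, Pr(θ_i > max θ_j, j ≠ i | data), with cut-offs 0.975 and 0.85. In the text, the trial stops early if "the probability that one treatment's median PFS is larger than the other's PFS exceeds 0.975"; the final criterion is "larger than the other's PFS exceeds 0.85". An arm is also dropped for efficacy "if the probability that the treatment's median PFS is larger than 3 months is less than 0.01". The maximum runs over every other arm, and no rule requires the selected arm to be open or tolerable.

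Efficacy is analysed by intention to treat, so a closed arm's patients stay in the PFS data. Section 2.8 says that the winner "will be considered the best regimen for further testing in a larger trial", provided that it compares well with historical controls. Tolerability is not named as a condition there. The tabled scenarios vary only the true medians and the accrual rate; none includes a toxicity closure.

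**The concern.** The safety rule and the selection rule do not refer to each other. Followed literally, two results are possible. The trial can declare superior, and even stop early for, a regimen that its own safety rule has closed. And an open arm that clearly beats the other open arm can go unselected because it must also beat a regimen to which patients can no longer be assigned. Either would affect the primary conclusion in just those trials where the safety rule has acted. The published operating characteristics give no information on this case.

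**Working it through.** **Inputs (Section 11.2).** Prior (2.009, 3.027) on each arm's median PFS, read as inverse gamma with mean 3.027/1.009 = 3.0 months. First 30 patients randomized equally, then adaptively with minimum probability 0.1 and tuning parameter 1. "A minimum of 30 and a maximum of 135 patients will be accrued", with 6 months of further follow-up. P_L = P_L* = 0.01, P_U = 0.975, P_U* = 0.85, θ_min = 3, accrual 3 or 5 per month. Exponential PFS is assumed, so with d events and total exposure T the posterior is inverse gamma (2.009 + d, 3.027 + T ln 2).

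**Reproducing the tables (1,000 runs per case).** Probability of selecting the best arm, simulated (tabled):

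| Scenario | 3/month | 5/month |
|---|---|---|
| 2 (3/4/5) | 0.531 (0.54) | 0.517 (0.492) |
| 3 (3/5/7) | 0.764 (0.758) | 0.771 (0.745) |
| 4 (3/3/7) | 0.995 (0.995) | 0.995 (0.997) |
| 5 (3/4/7) | 0.956 (0.96) | 0.947 (0.949) |

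The standard error of a difference is about 0.02, so the agreement is adequate.

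**Do suspended arms stay in the maximum?** Scenario 6 at 3/month helps. Early selection totals only 0.001, so the stopped-early column there reflects suspensions: 0.819 + 0.802 + 0.806 = 2.427 arms per trial. If every trial ended with two or three arms suspended, 3 − 2.427 = 0.573 of trials ended with one arm open. Were suspended arms removed, that sole arm would have probability 1 and be selected. The table shows total selection of only 0.025 + 0.015 + 0.012 = 0.052. Simulation that keeps suspended arms in the comparison and ends the trial when one arm is open gives 0.019 + 0.014 + 0.025 = 0.058. The tabled software therefore appears to keep suspended arms in.

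**Arm 3 closed at its first 10 patients, medians 3/5/7, rules as written.**

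| Case | Closed Arm 3 selected | Arm 2 selected |
|---|---|---|
| 3/month, accrual continues with one arm open | 0.444 (0.273 early) | 0.054 |
| 3/month, trial ends when one arm is open | 0.319 | 0.058 |
| 5/month, accrual continues with one arm open | 0.422 | 0.051 |

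The standard error of 0.444 is √(0.444 × 0.556/1000) = 0.016. Over repeated runs and both ending rules at 3/month, the ranges are about 32-44% for the closed arm and 4-8% for Arm 2.

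**Why neither arm may be selected.** Suppose that all 10 patients on the closed arm have progressed, with data at a 7-month median (T ln 2 = 70), and likewise 84 patients on Arm 2 at a 5-month median (T ln 2 = 420). The posteriors are inverse gamma (12.009, 73.027), mean 6.6 and SD 2.1, and (86.009, 423.027), mean 5.0 and SD 0.5. Then Pr(θ_3 > θ_2) = Pr(F < (73.027/423.027) × (86.009/12.009)) = Pr(F < 1.236) with 24.0 and 172.0 degrees of freedom, which is 0.78. That is below 0.85 for Arm 3, and Arm 2 can have at most 0.22.

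**How much is due to freezing the arm at 10 patients?** Selection of Arm 2 at 3/month:

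| Medians | Arm 3 open | Arm 3 closed at 10 |
|---|---|---|
| 3/5/7 | 0.019 (tabled) | about 4-8% |
| 3/5/5 | about 21-26% | about 21-27% |
| 3/5/4 | about 51-53% | about 41-43% |

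Freezing costs Arm 2 something only in the last row, about 8-12 points.

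**Chance of closure.** One third of 10 means at least 4 patients. Ignoring the dose-reduction condition, P(X ≥ 4), X ~ Bin(10, p), is 0.12, 0.35 and 0.62 at assumed true DLT rates of 0.2, 0.3 and 0.4.

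**Removing the closed arm.** At unchanged thresholds, Arm 2 is selected in about 94-96% of trials at 3/5/7, but with medians 3/3/3 one of the two open arms is selected in 0.244 + 0.240 = 0.484 (about 46-50% over runs). The tabled three-arm totals are 0.054 + 0.051 + 0.061 = 0.166 at 3/month and 0.040 + 0.046 + 0.055 = 0.141 at 5/month. With 0.995 early and 0.95 final, null selection is about 15-20% and Arm 2 is selected in about 82-84% at medians 3 and 5.

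**The case against.** The strongest reply has five parts.

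- **Closure may be rare.** The temozolomide triple has its own phase I, which accepts at most 1 of 6 patients with DLT, and the phase II rule closes an arm only if toxicity persists despite dose reduction. This stands: every selection figure here is conditional. A reader might take the intolerable triple in Section 2.11 as a forecast. That regimen contained carboplatin, and the section attributes the problem mainly to overlapping carboplatin and vorinostat toxicity, so it says nothing firm about this one.
- **The frozen arm does not itself block Arm 2.** A reader might infer that a wide posterior from 10 patients is the main obstacle. The open-versus-closed comparison refutes that at 3/5/7 and 3/5/5. Arm 2 is seldom selected mainly because the rule asks for the best of all three. What remains is that one of the three can no longer be used.
- **Setting 4-8% against 94-96% is not like for like.** The higher figure comes from thresholds that have lost error control, so it does not measure the cost of the present rule.
- **Selection is not advancement.** It means longer PFS; toxicity is tabulated by arm, and Kaplan-Meier, log-rank and Cox analyses remain. True, but an early stop for a closed arm still ends the trial before the open arms finish accruing.
- **Appendix H may cover it.** Possible, as it was not supplied. Section 11.2, however, states the selection rules without any such exclusion.

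**Conclusion.** The gap is real. The rules as written allow a toxicity-closed arm to be named superior and keep it as a comparator. With medians 3/5/7, closure of Arm 3 at 10 patients and accrual of 3 per month, this happens in about 32-44% of trials. The range depends largely on whether the trial ends when one arm is open, which the text does not say. Arm 2 is selected in about 4-8%. The size rests on exponential PFS, the inverse-gamma reading of the prior, closure at the first look, and the closed arm having the longest PFS. At 3/5/5 the closed arm is selected in about 10%. None of these is an unconditional probability, since the documents give no DLT rate from which the chance of closure could be derived.

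**What to change.** State in Sections 9.1 and 11.2 that, from closure for toxicity, an arm cannot be selected and that Pr(θ_i > max θ_j) is computed over the remaining arms only. Make Appendix H and the randomization website agree with this. Set separate two-arm thresholds by simulation so that null selection is no higher than the tabled three-arm total (0.166 at 3/month, 0.141 at 5/month), and report those operating characteristics with closure included. The pair 0.995 and 0.95 is only a starting point, because its null selection of about 15-20% may exceed those limits. State also whether the trial ends when one arm is open.

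The cost is a sentence in each section, a check or change of the website's calculation, and a short simulation. The downside is lower power than unchanged thresholds would give: about 82-84% selection of Arm 2 at medians 3 and 5 with the starting pair, against about 94-96%. No dose or toxicity criterion changes.

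### The planned log-rank and Cox comparisons ignore adaptive allocation, arm suspension and continuous stopping: a 5% three-arm PFS log-rank test would reject in about 13-16% of trials with identical arms

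*Combined protocol and SAP*

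**What the plan says.** Section 11.2 selects the winning arm by a Bayesian rule on PFS and then adds conventional analyses.

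- **Allocation.** "Patients will be randomized fairly among the three arms at the start of the trial (for the first 30 patients"); after that "the randomization will become unbalanced in favor of the" arm with the better failure times so far. The design table sets a floor of 0.1 and a tuning parameter of 1.
- **Size and follow-up.** "A minimum of 30 and a maximum of 135 patients will be accrued". Follow-up then runs for a further 6 months.
- **Stopping.** "The trial will be stopped early and a treatment selected as being" better once its posterior probability of being best passes 0.975. At full accrual the threshold is 0.85. The data are evaluated as each new patient enters.
- **Suspension.** The stopping-rule table closes an arm to accrual if Pr(best) < 0.01 or Pr(median > 3 months) < 0.01.
- **Conventional analysis.** PFS and OS get Kaplan-Meier curves and a Cox model with covariates, and "The log-rank test will be performed to test the difference in time-to-event distributions between patient groups".

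No significance level is given, nor whether the test is three-arm or pairwise, and nothing adjusts for the adaptive features. The tabled operating characteristics cover only the Bayesian selection rule. For toxicity summaries the same section rules out formal testing. It makes no such statement for PFS or OS.

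**The concern.** A standard log-rank p-value assumes that the numbers at risk and the time of analysis do not depend on the treatment comparison itself. Here they do. An arm that does badly by chance gets fewer patients, or none while suspended, so its poor early result is diluted slowly. An arm that does well by chance can end the trial at that moment. Both push apparent differences between equal arms away from zero, and the ordinary p-value takes no account of it.

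At stake is how the PFS comparison is read. Section 2.8 sends the winner to a larger trial if it compares favourably with historical controls. A nominally significant log-rank result for that arm would support the choice, although chance produces such results far more often than the p-value implies. The selected arm's estimated median is also biased upward, because the arm was picked for looking best.

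**Working it through.** **Inputs from 11.2.** Median PFS 3, 3 and 3 months (scenario 1); 30 patients allocated equally; maximum 135; 6 months of follow-up; accrual of 3 or 5 per month; the allocation and stopping settings above; prior parameters (2.009, 3.027) for each arm.

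**Assumptions.** PFS is exponential. The prior is inverse gamma on the median; this is inferred from its mean, b/(a − 1) = 3.027/1.009 = 3.0 months, which equals the historical median. Allocation is proportional to Pr(best) to the power 1. The test level is two-sided 5%. Appendix H, which holds the technical details, is not in the available text.

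**Model.** With d events and total follow-up T in an arm, the posterior of its median is inverse gamma (2.009 + d, 3.027 + T·ln 2). Pr(best) was computed by numerical integration at every new patient after the 30th. Main settings used 5,000 to 7,000 trials. The Monte Carlo standard error is √(0.15 × 0.85/5,000) = 0.5 points, or 0.4 points with 7,000.

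**Step 1: reproduce the plan's figures** (suspended arms may reopen).

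| Quantity | Plan | Simulated |
|---|---|---|
| Scenario 1, 3/month: selected, per arm | 0.054, 0.051, 0.061 | 0.054, 0.053, 0.051 |
| Scenario 1, 3/month: stopped early | 0.081-0.083 | 0.076-0.084 |
| Scenario 1, 3/month: patients per arm | 43.7-43.8 | 43.4-44.0 |
| Scenario 1: trial length, 3 and 5/month | 49.5 and 31.8 | 49.5 and 31.9 |
| Scenario 2, 3/month: best arm selected | 0.54 | 0.537 |
| Scenario 2, 5/month: best arm selected | 0.492 | 0.52-0.53 |
| Scenario 4: best arm selected, 3 and 5/month | 0.995 and 0.997 | 0.997 and 0.993 |

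Scenario 6 (all medians 1 month) was run only with permanent suspension and did not match: length 11.4 and 7.2 months against 10.3 and 6.28. Any selection was below 1%, against table sums of 0.025 + 0.015 + 0.012 = 5.2% and 0.020 + 0.022 + 0.024 = 6.6%. That scenario does not bear on the 3-month null.

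**Step 2: three-arm PFS log-rank, identical arms, share with p<0.05.**

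| Setting | 3/month | 5/month |
|---|---|---|
| Full design, data cut at the stop | 14.4-15.7% | 15.4-15.8% |
| Full design, 6 months' follow-up also after an early stop | 14.3% | 13.7% |

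If suspended arms never reopen, the range is 12.6-15.0%. With equal allocation, no stopping and no suspension it is 5.9%. Separately coded runs of 2,000 to 3,000 trials per setting gave about 13-16%.

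**Step 3: where the excess comes from (3/month).**

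| Features switched on | Rejection |
|---|---|
| Adaptive allocation only | 8.1% |
| Early selection only | 8.4% |
| Both, no suspension | 10.1% |
| All rules (7,000-trial run) | 15.7% |
| Early selection and permanent suspension, equal allocation | 16.4% |

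Adding suspension accounts for (15.7 − 10.1)/(15.7 − 5.9) = 5.6/9.8, about 57% of the excess in that run.

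In the same run, 0.017 + 0.016 + 0.016 = 4.9% of trials selected an arm early, and 93.1% of those had p<0.05. Of the other 95.1%, 11.6% did. Check: 0.049 × 0.931 + 0.951 × 0.116 = 0.156, agreeing with 15.7% up to rounding. Trials that run to full accrual are therefore inflated too. Without suspension their rate is 5.9%.

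**Step 4: other tests.** Each pairwise PFS log-rank rejects in about 10-12% of null trials, and at least one of three unadjusted pairs in 22-24%. For OS, taken as PFS plus an independent exponential survival after progression with a 4-month median (an assumption), the three-arm test rejects in about 8-9%. The Cox model was not simulated. A Cox comparison of the same arms uses the same adaptively collected data.

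**The case against.** The best defence is that the log-rank test decides nothing. The winner is chosen by posterior probabilities whose behaviour was simulated, this is a phase II trial, and the next step is a larger one. The plan states no 5% level, and its reference to patient groups could mean groups defined by baseline factors. The simulation also rests on a model that the available text does not spell out.

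Much of this stands. The 5% level is an assumption, and no trial decision turns on the p-value. But the plan commits to the test for PFS, does not call it descriptive, and does not exclude arm comparisons. The model reproduces the plan's null scenario closely.

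A reader might infer more than the documents support:

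- **That the selection error is wrong.** It is a separate quantity. The scenario 1 table gives 0.054 + 0.051 + 0.061 = 16.6% and 0.040 + 0.046 + 0.055 = 14.1% for selecting any arm. These resemble the log-rank figures but say nothing about that test.
- **That OS is distorted as much as PFS.** OS drives neither allocation nor stopping, and its inflation is smaller.
- **That adaptive allocation is the main cause, or that a poor arm can never recover.** Allocation alone gives 8.1%. The rules suspend accrual, and the runs that match scenario 1 let arms reopen.
- **That the selected arm's median is inflated by a known amount.** The direction is clear, but the size depends on the estimator and the data cut.

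**Conclusion.** The point holds for the supporting PFS analysis. As written, a three-arm PFS log-rank test read at 5% rejects in about 13-16% of trials when the arms are identical, roughly three times the nominal rate (13/5 = 2.6; 16/5 = 3.2). Fixed equal allocation without stopping gives about 6%. Outcome-adaptive allocation, early selection and arm suspension all contribute, and suspension supplies much of the excess.

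The figure rests on exponential PFS, the inferred prior family and the assumed two-sided 5% level. Whether suspended arms reopen, and whether follow-up continues after an early stop, moves it only within about that range. For OS, 8-9% depends further on the assumed survival after progression. The Bayesian selection rule and its tabled operating characteristics are untouched. This is more than a missing detail, because the stated test gives p-values that are too small.

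**What to change.** Add a paragraph to 11.2 that does the following:

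- States that log-rank and Cox p-values comparing the arms will be referred to a null distribution obtained by replaying the full design (allocation, suspension and stopping) under a common median, using the software that produced the tables. Alternatively, it states that curves and hazard ratios will be reported descriptively, without p-values.
- If p-values are kept, gives the level and says whether the comparison is three-arm or pairwise. For OS, it states the survival model used in the replay.
- Notes that the selected arm's estimated median is biased upward by selection.

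The cost is a little computing and a less favourable p-value. Allocation, sample size and the selection rule stay as they are.

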7.0 ON-STUDY EVALUATION

- 7.1 CBC, differential and platelets will be performed weekly (± 3 days) for the first cycle. If no significant toxicity is seen, monitoring will be changed to every two weeks (± 3 days) during treatment and prior to each new cycle. In addition, all patients will have the following tests every 2 weeks (± 3 days) for the first cycle and then every cycle as well as prior to each new cycle if no significant toxicities are noted: PT, PTT, INR, total protein, albumin, calcium, phosphorus, magnesium, glucose, BUN, creatinine, sodium, potassium, uric acid, total bilirubin, alkaline phosphatase, LDH, SGPT, SGOT. All patients will have serum amylase, lipase, and lipid panel drawn every 2 cycles of treatment. Patients may also be evaluated with labs at any time clinically indicated.
- **7.2** Patients on treatment with enzyme-inducing antiepileptic drugs (phenytoin, phenobarbital, carbamazepine) will be evaluated with anticonvulsant levels as considered appropriate by the treating physician.
- **7.3** A Gd-DPTA MRI scan shall be done after each **2 cycles** of treatment prior to initiating the next cycle. MRI scans may also be done at any time clinically indicated.
- 7.4 Physical and neurologic examinations will be performed after cycle 1 and cycle2, and subsequently after each 2 cycles of treatment prior to initiating the next cycle. Patients will also be evaluated anytime their clinical situation demands an assessment.
- **7.5** All patients receiving cRA must be enrolled in the iPLEDGE program (see Appendix I). Before starting treatment, an "Exception Authorization for Oncology Patient" will be requested for women of childbearing potential (Appendix J). A negative serum pregnancy test will be obtained 24 hours before initiation of treatment with cRA. Once treatment has started, pregnancy testing and counseling should occur monthly. If pregnancy does occur during cRA treatment, the drug must be discontinued immediately and the treating physician notified. The treating physician will in turn notify the study chair immediately.
- 7.6 The MDASI-BT will be completed at the time of physical and neurologic exam, i.e. after cycle 1 and cycle 2, and subsequently after every 2 cycles of treatment prior to initiating the next cycle of treatment. (*)
- **7.7** All relevant information regarding drug doses, concomitant medications and doses, measurable lesions, tumor response, laboratory examinations, and

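### Toxicity is tabulated by arm with no common time window and no allowance for time on treatment, so crude percentages can lean against an arm with longer PFS

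*Combined protocol and SAP*

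**What the plan says.** Section 11.2 states: "Toxicity data will be summarized by frequency tables". It then says that "The association between the types and severity of toxicity and the treatment groups will be evaluated", and directly afterwards that "No formal statistical testing will be performed on these summary data". The toxicity set is as-treated: anyone who received treatment, "regardless of the eligibility nor the duration or dose of the treatment received". No exposure denominator, fixed window, per-cycle rate or time-to-first-event analysis of toxicity is described.

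Other sections that bear on the point:

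- **Treatment length.** Sections 5.2.1 and 10.0 continue treatment until progression or unacceptable toxicity. One year is planned, and longer treatment is allowed.
- **Follow-up.** The closing paragraph of Section 5.4.2.3 follows every patient for toxicity for at least 30 days after treatment ends.
- **Laboratory schedule (7.1).** "CBC, differential and platelets will be performed weekly (± 3 days) for the first cycle"; then "If no significant toxicity is seen, monitoring will be changed to every two weeks (± 3 days) during treatment and prior to each new cycle". Chemistry is every two weeks "for the first cycle and then every cycle as well as prior to each new cycle if no significant toxicities are noted".
- **Recording.** Section 9.1 has toxicity graded and recorded before each course.
- **Role.** Section 1.2 lists unexpected toxicity by arm among the secondary endpoints.

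**The concern.** A crude percentage of patients with a toxicity depends on the hazard and on how long patients are at risk. Here time at risk follows PFS, which is the primary endpoint and the outcome on which the arms are expected to differ. Two arms with the same monthly hazard can therefore show different percentages only because patients in one of them stay on treatment longer.

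At stake is how the secondary toxicity endpoint is read. Under Section 2.8 the winning regimen may go forward to a larger trial, and with no formal testing the raw percentages are all a reader has. A regimen that holds off progression could look more toxic than it is. Conversely, an arm that patients leave early because of toxicity could look less toxic than it is.

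**Working it through.** **The plan's own figures.** The plan gives no figure for the toxicity comparison. The design result that uses the same PFS medians is scenario 4 (3, 3 and 7 months), with stated probabilities of selecting the best arm of 99.5% and 99.7% at 3 and 5 patients per month. A 500-repetition reconstruction (exponential PFS, the stated prior and cut-offs) gave 99.4% and 99.8%. Its per-arm stopping frequencies in scenario 4 were lower than the plan's (at 3 per month, about 0.53 against 0.98 for the two 3-month arms) and are not used. The match supports reading 3 and 7 months as exponential medians; it says nothing about toxicity.

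**Inputs from the documents.** Medians 3 and 7 months (11.2); treatment to progression (5.2.1, 10.0); at least 30 days of follow-up (5.4.2.3).

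**Assumptions.** Exponential PFS; treatment capped at 12 months; 30 days taken as one month; every patient observed to the end of follow-up; the same toxicity hazard in both arms, 0.02 to 0.30 per month.

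**Time on treatment.** With λ = ln 2 / median, λ = 0.2310 (3 months) and 0.0990 (7 months). Mean time on treatment is (1 − e^(−12λ))/λ = 4.06 and 7.02 months.

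**Share with at least one event.** Let h be the month-1 hazard and kh the hazard afterwards. Every patient is followed for at least one month, so

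share = 1 − e^(−h) · B(kh), where B(x) = λ/(λ+x) + [x/(λ+x)] · e^(−12(λ+x)).

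Example with h = 0.05 and k = 1:
- Median 3: B = 0.8221 + 0.1779 × 0.0343 = 0.8282; share = 1 − 0.9512 × 0.8282 = 21.2%.
- Median 7: B = 0.6645 + 0.3355 × 0.1673 = 0.7206; share = 1 − 0.9512 × 0.7206 = 31.5%.

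| Pattern | h per month | Median 3 | Median 7 | Ratio |
|---|---|---|---|---|
| Constant (k = 1) | 0.02 | 9.4% | 14.5% | 1.54 |
| | 0.05 | 21.2% | 31.5% | 1.48 |
| | 0.10 | 36.3% | 50.8% | 1.40 |
| | 0.30 | 67.7% | 81.1% | 1.20 |
| Later hazard 10% (k = 0.1) | 0.10 | 13.1% | 15.6% | 1.19 |
| | 0.20 | 24.3% | 28.6% | 1.18 |
| | 0.30 | 34.1% | 39.5% | 1.16 |
| Month 1 only (k = 0) | 0.20 | 18.1% | 18.1% | 1.00 |

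With equal medians (scenario 1) there is no difference under any pattern.

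**Common window.** Counting cycle 1 only, at h = 0.05 and without follow-up, the shares are 4.1% and 4.3%.

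**Pooled rates.** A single first-event rate per month at risk returns the true hazard in both arms when the hazard is constant. It does not when toxicity is front-loaded. With h = 0.20, k = 0.1, a 12-month cap and no follow-up, it is 0.065 (median 3) against 0.049 (median 7) at identical hazards. The longer-PFS arm then looks about 25% less toxic (0.049/0.065 = 0.75). Split by period, both arms return 0.20 and then 0.02.

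**The case against.** The strongest reply is that these are descriptive tables. Section 11.2 rules out formal testing on them, the winner is chosen on PFS, and safety stopping is a separate check of dose-limiting toxicity after every 10 patients per arm. All of that stands and limits the point to interpretation.

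A second reply is that toxicity may be early. Section 2.3.4.1 says most dose-limiting toxicities with oral vorinostat came in the first month, and doses are reduced after toxicity. This narrows the effect, but removes it only if later toxicity is nil. The statement also covers only vorinostat and only dose-limiting events.

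Some stronger readings are tempting but are not supported:

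- **That collection stops with treatment.** Follow-up lasts at least 30 days beyond it.
- **That thinner laboratory monitoring causes the excess.** The schedule is the same in all arms, thinning depends on no significant toxicity having been seen, and toxicity is still recorded before each course. Sparser late testing finds fewer late events, so it dampens the excess. Expected blood counts are about 10.2 against 16.8 per patient (ratio 1.65); weekly testing throughout would give 17.2 against 30.2 (1.76).
- **That the longer-PFS arm must look worse by construction.** This needs both unequal PFS and continuing toxicity. An arm that patients leave early because of toxicity is distorted the other way.
- **That the plan forbids accounting for exposure.** The clause about duration and dose defines who enters the analysis set.
- **That Section 2.10's aim of least toxicity refers to these tables.** It concerns symptom burden measured by MDASI-BT.

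**Conclusion.** The point holds in limited form. The plan compares toxicity between arms by crude percentages while time at risk follows PFS, and it provides nothing to separate the two. For medians of 3 and 7 months, the widest contrast among the design scenarios that include the 3-month reference, the longer-PFS arm shows 5 to 16 percentage points more patients with an event under a constant hazard. The excess is 0 to 5 points when the later hazard is 0 to 10% of the month-1 hazard. These sizes rest on assumed hazards, equal between arms, and on the 12-month cap; the documents supply none of these for the combinations studied. Arm selection and the safety stopping rule are unaffected. It is an inexpensive improvement to the reading of a stated secondary endpoint, and worth making.

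**What to change.** In Section 11.2, keep the frequency tables and add, by arm:

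1. **Time on treatment.**
2. **A cycle-1 toxicity table**, as a common window.
3. **Cumulative incidence of first grade 3 or higher toxicity**, with end of treatment follow-up for progression or death as a competing event, read at common early time points. Beside it, show first-event rates per cycle at risk, separately for cycle 1 and for later cycles. These rates should not be pooled across periods, for the reason shown above.

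State that between-arm differences in the all-time frequencies will be interpreted alongside these.

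The cost is SAP wording and a few extra tables from data already collected, with no new visits and no change in sample size. Cycle 1 will contain fewer events. It should not be the sole basis for comparison, because Section 5.4.2.3 allows the temozolomide dose to change from cycle 2, so cycle 1 may not represent later cycles. Sections 5.1.2 and 5.4.2.3 also give different temozolomide doses for the start of treatment; they must be reconciled before a cycle-1 table can be interpreted.
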